Hypothesis 3: The use of both BoNT-A injections and supervised gait retraining will be more effective than either treatment alone. In adult active duty service members with CECS, the use of both BoNT-A injections and supervised gait retraining returns service members to full duty, including being able to complete their service-specific military physical tests, sooner and for sustained longer periods than SGR or BoNT-A injections alone.

Process for Hypothesis 3: Evaluate functional improvements in Group 4 as compared to Groups 2 & 3 via the subjective and objective data variables described in protocol sections 10.1 & 10.2. Assess the ability of all study groups to complete a 2-mile run and to compete their required service-specific physical fitness testing within the established standards at 8 weeks, 3 months, 6 months, and 12 months post-study injection.

9.4 Study Design:

Describe study design in one to two sentences (e.g., prospective, use of existing records/data /specimens, observational, cross-sectional, interventional, randomized, placebo-controlled, cohort, etc.). Specify the phase – Phase I, II, III, or IV – for FDA-regulated investigational drug research

Multi-site, single-blinded randomized placebo-controlled study

9.5 Target Population:

Describe the population to whom the study findings will be generalized

Adult military beneficiaries diagnosed with Chronic Exertional Compartment Syndrome (CECS)

9.6 Benefit to the DoD:

State how this study will impact or be of benefit to the Department of Defense

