Those randomized into a BoNT-A injections group (i.e., Group 3 or 4) will receive up to 2 injections per affected anterior and/or lateral compartment. Per standard clinical procedure, a solution of 25 units of Botulinum toxin, per 1 mL of normal saline will be used for each injection. Standard aseptic technique will be followed. Insertion into the correct compartment will be accomplished using ultrasound guidance. The anterior and/or lateral compartments will each be separated into thirds measuring from the tibial plateau to the head of the calcaneus. Injections will be given at approximately 1/3 the distance from the tibial plateau for the proximal injection and 2/3 the distance from the tibial plateau for the distal injection. Injections will only be given in the compartments that have elevated compartment pressure using the standard Pedowitz criteria: 1) a pre-exercise pressure greater than or equal to 15 mmHg, 2) a 1 minute post-exercise pressure of greater than or equal to 30 mmHg, or 3) a 5 minute post-exercise pressure greater than or equal to 20 mmHg.¹² If the lateral compartment is affected, a total of 50 units of botulinum toxin will be given. The proximal aspect of the peroneus longus and brevis is approximately 1/3 the distance from the tibial plateau and it will receive 25 units of botulinum toxin A. The distal aspect of the peroneus longus and brevis is approximately 2/3 the distance from the tibial plateau and this area will also receive 25 units of botulinum toxin A. If the anterior compartment is affected, a total of 50 units of botulinum toxin will be given; 25 units to the proximal anterior compartment and 25 units to the distal anterior compartment.^{1,2}

Of note, CECS mainly affects the anterior and lateral compartments and is rarely seen in the superficial posterior or deep posterior areas; thus, the anterior and lateral compartments will be the focus of this study and patients with concomitant or isolated posterior compartment symptoms will not be included in this study. Participants who receive BoNT-A injections will be provided with a Post-Injection After Care Handout (Appendix O). The information provided to the participant after the injection are observed signs and/or symptoms that could occur with receiving either a BoNT-A or saline injection. This handout is not likely to expose the blinding of the injection that the participant receives as part of the study.

Saline Injections:

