Those randomized into the normal saline groups will receive injections in the identical manner above, using the appropriate amount of solution (0.5 mL to 1 mL). The syringes will be prepared by the clinical research staff using standard sterile techniques, out of view of the participant to ensure appropriate blinding.

Study Injection Documentation (both groups):

All injections will be done under ultrasound guidance. The provider will use the ultrasound machine to identify bony landmarks of the tibial plateau and will then move the probe laterally towards the fibular head to identify the anterior and lateral compartments of the lower leg. Distally, the provider will identify the midway area between the fibular head and the tip of the lateral malleolus.

Study injection administration to the participant will be documented using a Treatment Documentation CRF (Appendix N). This Treatment Documentation CRF will be entered into REDCap. Study injection administration will also be documented in the participant's electronic medical record following standard procedures.

Supervised Gait Retraining (SGR):

The SGR course will focus on mid-forefoot strike, increasing their cadence while shortening their stride, and decreasing their peak ground reaction force. This program has been developed by physical therapists at West Point and the Army DPT program in Fort Sam Houston. This program uses group physical therapy sessions, lower extremity exercises, home exercise training drills, and advanced wearable technology to effectively change key gait parameters.

Supervised physical therapy sessions will be documented using a SGR Physical Therapy Documentation CRF (Appendix M). This SGR Physical Therapy Documentation CRF will be entered into REDCap. Study supervised physical therapy sessions will also be documented in the participant's electronic medical record following standard procedures. Participants in the SGR group(s) will also be sent home with a handout (Appendix L) explaining exercises that can/should be done from home to supplement their supervised physical therapy sessions.

Home Based Gait Retraining:

The HBGR will focus on increasing cadence, running softer and increasing endurance strength with exercises for the lower extremity. A handout (Appendix L) explaining desired exercises and gait retraining will be given to each participant with daily exercise instructions. Participants will be contacted weekly as a reminder to complete their home program.

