If the participant has a change of duty station (permanent or temporary) and/or cannot make an in-person visit, the following will be collected using Appendix E, Follow Up Data Collection Sheet: relevant medical and service history and demographic questions including age, gender, body mass index, symptoms duration, location, and characteristics, treatment history, work status, military rank, branch of service, length of service, limited duty/profile days, occupational specialty, concomitant medical conditions, activities provoking symptoms, location of symptoms, footwear characteristics and orthosis use, etc., numeric pain rating scale (NPRS), University of Wisconsin Running Injury and Recovery Index (UWRI), Single Assessment Numerical Evaluation (SANE), Patient Specific Functional Scale (PSFS) will also be assessed. This may be collected with electronic mail, postal mail, and/or telephone communication with the participant.

Many of the activities in this study are performed regularly as part of standard of care for patients being seen for lower extremity CECS. Please see Appendix H: Data Collection Schedule for details on which activities are standard of care.

Study Completion:

Participants' study completion or withdrawal will be documented on the Study Completion CRF (see Appendix S).

Additional Considerations - COVID-19:

For as long as deemed clinically appropriate, there will be additional precautions in place to ensure the health and safety of research staff and research participants and to combat the spread of COVID-19. Research staff will closely follow all current local clinical guidelines regarding the use of PPE, hand washing, disinfecting of equipment, proper distancing, etc. Additionally, the study team will reduce the need for in-person research-specific visits when possible. For participants assigned to one of Standardized Gait Retraining (SGR) groups, some of their clinical follow ups during the physical therapy period may be conducted and documented as a video/telehealth encounter. For participants assigned in all groups, the 24-month follow up visit which requires no physical examination can be conducted remotely, meaning the participants can complete the questionnaires electronically, over the phone, or hard copy via mail all while remaining at home.

Study Blinding:

Participants will be blinded to assigned treatment arm (i.e., saline vs. BoNT-A injection) until 3 months post-injection.

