Blinding will be revealed to the participants after all the components of the 3 month follow-up visit have been completed. Participants who are not satisfied with their treatment results and/or who are unable to complete a 2-mile run without producing pain and/or symptoms will be offered the option to receive BoNT-A injections and/or Supervised Gait Retraining if they had not received those active treatments.

At the 6 month follow-up visit, participants who are still not satisfied with their treatment results and/or still unable to complete a 2-mile run will be offered any remaining treatment option, including surgical fasciotomy which is offered as standard of care. Participants who express interest in surgical fasciotomy will be referred to an orthopaedic surgeon who will dictate and guide this treatment option. Further details and scheduling will be per the orthopaedic surgeon's recommendations. Patients who cross over to alternative treatment options (including surgical fasciotomy) will remain in the study and will continue to follow up with the research team at the intervals listed above.

Data Entry:

With the exception of the Intake CRF which collects participant contact information, all coded research data will be entered into REDCap, an encrypted, access controlled, password protected electronic data capture and management system housed on a DoD server and maintained by the Uniformed Services University (USU). No PII will be entered into REDCap. See Appendix J for additional information on REDCap. See Appendix I for a PDF copy of the REDCap forms for this study.

Additional Info - MIRROR/USU:

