There will be appropriate data sharing agreements in place between the data owner(s) (e.g., DHA for AHLTA) and the Walter Reed National Military Medical Center (WRNMMC), as well as the Uniformed Services University (USU) and all appropriate parties involved in the handling of data (e.g., The Geneva Foundation).

10.2 Data Collection:

Describe all the data variables, information to be collected, the source of the data, and how the data will be operationally measured.

Please see attached Data Collection Schedule (Appendix H).

The local study team will collect study data directly from the study participant, from their attending provider or, where applicable, from the participant's medical record (i.e., relevant medical and treatment history and relevant clinical notes) and record it on paper CRFs (see Appendixes A-F). Study completion will be documented (see Appendix S). The completed paper CRFs will serve as source documents for this study. Participants may also enter study data directly into REDCap using a coded survey link. In these cases, the completed eCRFs will be printed and stored in the participant's research files and serve as source documents. Other source documents include relevant laboratory results (i.e., hCG urine test) and relevant clinical notes which will be printed, redacted, and stored in the participant's research file.

With the exception of the Informed Consent Form, HIPAA Authorization, and Intake CRF (Appendix B) which collects contact information, all paper CRFs will be identified using a unique study ID only, and not by the participant's name, social security number, DoD ID, or other protected identifier.

The primary outcome will be functional improvement via statistical changes in the Balance Error Scoring System (BESS), University of Wisconsin Running Injury and Recovery Index (UWRI), Single Assessment Numerical Evaluation (SANE), Patient Specific Functional Scale (PSFS), Global Rate of Change (GROC), objective data from the gait and run analyses (e.g., average vertical load rate, cadence, foot pattern strike, etc.), ability to return to full active duty, and ability to complete a 2-mile run. Full active duty is defined as meeting all service specific requirements of physical training and ability to complete work duties with either no pain or pain that is tolerable as determined by the patient.

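### Section 10.1 has the injection charted by standard procedures without masking, so an ordinary entry could unblind the participant before the 3-month visit is complete

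*Combined protocol and SAP*

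**What the plan says.** Section 9.4 describes the trial as a "Multi-site, single-blinded randomized placebo-controlled study". Section 10.1 (Study Blinding) defines the blind: "Participants will be blinded to assigned treatment arm (i.e., saline vs. BoNT-A injection) until 3 months post-injection". It ends as follows: "Blinding will be revealed to the participants after all the components of the 3 month follow-up visit have been completed".

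Section 10.1 (Study Injection Documentation, both groups) has the injection recorded twice. One record is the Treatment Documentation CRF (Appendix N), which goes into REDCap. For the other: "Study injection administration will also be documented in the participant's electronic medical record following standard procedures".

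Therapy is charted in the same place: "Study supervised physical therapy sessions will also be documented in the participant's electronic medical record following standard procedures". Section 10.2 lets the local study team take data "from the participant's medical record (i.e., relevant medical and treatment history and relevant clinical notes".

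Section 10.1 names two safeguards for the blind. On preparation: "The syringes will be prepared by the clinical research staff using standard sterile techniques, out of view of the participant to ensure appropriate blinding". On the aftercare handout: "This handout is not likely to expose the blinding of the injection that the participant receives as part of the study".

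**The concern.** The participant blind is the only blind in the trial. It covers the 8-week and 3-month visits, and these are also the last visits before participants are told their injection and may be offered the treatments they did not receive. They are therefore the only follow-up visits that are both blinded and free of planned crossover.

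The plan protects this period at the syringe and the handout, then sends the injection to the ordinary medical record under routine charting rules. If the entry names the agent, the blind depends on nobody passing its content to the participant for about 3 months. A participant who learns the arm may rate symptoms and function differently, or push harder or less hard on the treadmill. Either response would move the BoNT-A comparisons for reasons other than the drug.

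**Working it through.** No figure in the plan needs reproducing. The check sets the relevant sections side by side.

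1. **What the rule produces.** Section 10.1 says the entry follows standard procedures and does not give its content. Section 9.2 says every performance site already offers BoNT-A injections for CECS as standard of care, so a routine way of charting them can be presumed to exist. Section 18.2 says the investigational pharmacy does not dispense and that a physician or nurse prepares the BoNT-A. No pharmacy-coded product is described that would give the person charting a masked label to copy. An entry naming the agent is the expected result, though this is an inference.

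2. **Whether anything masks it.** The supplied text contains no rule for a neutral entry, a restricted note or delayed release. The redaction in Sections 10.2 and 10.14 applies to printed notes placed in the research file and leaves the live record as it is. The two named safeguards cover preparation and the handout only.

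3. **How it could reach the participant.** There are two routes: the participant sees the note, or a clinician who has read it mentions the agent. Therapy can start from 2 weeks after injection (Section 10.1) and is charted in the same record, so clinicians use that record during the blinded period. The documents do not say whether participants can view their record.

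4. **Which results are exposed.** At 8 weeks and 3 months the participant completes NPRS, UWRI, SANE, PSFS and GROC and is asked about satisfaction; all are self-rated. The treadmill test is self-paced and ends at cessation or two miles, so expectation can act on it as well. UWRI, SANE, PSFS, GROC and the 2-mile run are listed in the primary outcome (Section 10.2). The comparisons affected are those that differ by injection within the same gait programme: Group 3 v 1 and Group 4 v 2. Group 2 v 1 has saline on both sides, so the agent does not differ between its arms.

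5. **Size.** On a scale score, the bias is roughly the share of participants who learn their agent multiplied by the shift that this causes in the between-arm difference. The documents give neither quantity, so no size follows from them.

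**The case against.** The strongest reply is that the text never says the entry names the agent. The sentence speaks neutrally of study injection administration, under a heading covering both groups. Appendix N is not available, and the consent pages were removed before review, so a masking instruction in either cannot be excluded. This stands: a reader might infer that the record does show BoNT-A or saline, and the documents support only that an ordinary entry would be expected to.

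Second, the trial is single-blind. A reader might infer that therapists, study staff or other clinicians who read the note thereby break the blind. They do not, because only participants are blinded and research staff already prepare the syringes. Those readers matter only as a possible channel to the participant.

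Third, not every outcome is exposed to the same degree. Balance testing and gait measures such as load rate and cadence are less open to expectation than questionnaires, and the sample size in Section 11.5 rests on passing a 2-mile run. This narrows the point to the self-rated scales and the run, where effort matters.

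Fourth, participants may guess their arm anyway. In the case series cited in Section 9.2, 11 of 16 patients had reduced strength after BoNT-A. That is fair, but a possible guess is weaker than a written statement of the agent, and only the latter is easily prevented.

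**Conclusion.** The point holds as a gap in how the blind is protected. Following Section 10.1 as written opens a direct route to unblinding in the only blinded, pre-crossover period, and nothing in the supplied text closes it. This rests on two assumptions: that a standard entry names the agent, and that its content can reach the participant before the 3-month visit is complete. The first is well supported by Section 9.2. The documents leave the second open.

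A reader might want to attach an inflated false-positive rate. The arithmetic can be run, but it does not measure this trial. Suppose a share q learn their agent and this shifts the between-arm difference by d SD. With 120 per group, SE = √(2/120) = 0.129 SD and bias = q × d. The two-sided false-positive rate is P(Z > 1.96 − bias/SE) + P(Z < −1.96 − bias/SE).

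- q = 10%, d = 0.3: bias 0.03 SD, rate 5.6%
- q = 50%, d = 0.5: bias 0.25 SD, rate 49%

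That span comes entirely from assumed inputs. The model is for a continuous mean, whereas Section 11.1 specifies logistic regression, and it does not separate the record from other ways of learning or guessing the arm. The change is justified because the route is direct and cheap to close; no estimated size is needed to support it.

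**What to change.** Replace the sentence on the electronic medical record in Section 10.1 with a rule such as:

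*Until all components of the participant's 3-month visit are complete, the injection is entered in the medical record in the same neutral words in both groups (for example: CECS study injection, BoNT-A or saline, masked), or the note is restricted from participant view. The agent is recorded on the Treatment Documentation CRF and added to the medical record at unblinding.*

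Confirm that Appendix N has a field for the agent. If sites already use a masked entry, or if participants cannot see these notes, say so in Section 10.1. Note that restricting participant view leaves the clinician route open, whereas a neutral entry covers both routes.

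The study team already knows the allocation and can disclose it to a treating clinician when needed. How that is handled for safety is for the sponsor to set.

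The cost is one changed passage in the protocol and a note template at each site. The downside is that, before the 3-month visit is complete, outside clinicians must contact the study team to learn the agent. The change cannot help participants who have already been unblinded.

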A newer proposed treatment for CECS is the intramuscular administration of botulinum toxin A (BoNT-A) into the muscles of the involved compartment(s). BoNT-A is FDA approved for intramuscular, intradetrusor, or intradermal use for muscle spasticity, migraine headaches, detrusor instability and severe forehead lines, lateral canthal lines, and glabellar lines in adults. A 2013 case series studying botulinum toxin injections for CECS demonstrated normalized intramuscular pressure up to nine months post-injection in 87.5% (14/16) of patients, and exertional pain was completely eliminated in 94% (15/16) of patients. Eleven patients experienced reduced muscle strength that was without functional consequences and transient resolving within 3 months. Only 1 of the 16 patients complained of new posterior leg pain that did not appear to be related to BoNT-A injections. There were no other adverse effects reported.¹ An additional 2016 case report showed effective pain and paresthesia relief from CECS after 1 set of injections for a recreational female athlete. In this report, the patient's symptoms resolved within 1 week. More importantly, she was able to return to full recreational activity within 4 weeks, with no return of symptoms throughout the 14 months of follow up without any weakness or adverse effect.²

Military sports medicine clinics at Fort Belvoir Community Hospital (FBCH) and the Uniformed Services University (USU) as well as the Department of Physical Medicine & Rehabilitation at Walter Reed National Military Medical Center WRNMMC) currently utilize BoNT-A (trade names BOTOX® or Xeomin®) injections for the non-surgical treatment of CECS. All of our performance sites currently offer BoNT-A (trade names BOTOX® or Xeomin®) injections as standard of care non-surgical treatment options for CECS.

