At 8 weeks (+/- 1 week), 3 months (+/- 2 weeks), 6 months (+/- 2 weeks), and 12 months (+/- 2 weeks) post-injection, participants will undergo Balance Error Scoring System (BESS) testing, objective foot parameters, ankle strength, range of motion (ROM), ankle brachial index (ABI) blood pressure, and palpation tests, and a gait and run analysis using advanced wearable technology as part of a self-paced treadmill test until cessation or the successful completion of a two-mile run (whichever occurs first). A gait analysis Data Collection CRF (Appendix R) will be used to collect some of the gait analysis from the advanced wearable technology and will be completed after the participant's visit.

Participants will also be asked about involvement in non-study related activities and treatments including acupuncture/acupressure, aquatics, anti-inflammatory/pain medication, athletic taping, change in running shoes, chiropractor, dry needling, electrical stimulation, foot orthotics, gait retraining, ice pack/massage, massage, physical therapy, strengthening, stretching, yoga, and other treatments.

Intramuscular compartment testing of participant's anterior and lateral compartments will be re-tested at 6 months (+/- 2 weeks) post-injection. The same compartments tested at baseline or at a previous test 6 months prior to consent of the study, will be recollected at the 6 month time point.

Results of the in-person clinical assessments and the intramuscular compartment testing will be recorded in the Follow Up Data Collection CRF.

Overall, the 8 week, 3 month, 6 month, and 12 month follow up activities will take approximately 2.5 hours each and the 24 month follow up activities will take approximately 30 minutes each.

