Secondary outcomes will include pain reduction according to the Numeric Pain Rating Scale (NPRS), ability to complete service specific military physical training requirements, and patient satisfaction. To assess patient satisfaction, patients will be asked if they were or were not satisfied with intervention at each follow up time point.

This will be an intention to treat study and additional data that will be collected via the Demographics CRF (Appendix C) and Baseline Data Collection CRF (Appendix D) includes:

- Standard Demographics (e.g., Age, Sex, military occupational specialty, height, weight, BMI, MOS)
- Length of military service
- Symptom duration (including length of limited duty, military profile)
- Previous Treatments
- Time to diagnosis

- Concomitant medical conditions
- Footwear characteristics and orthosis use
- Activities provoking symptoms, and perceived exertion (Borg) tolerance
- Duration of symptoms when present
- Performance on military fitness tests
- Ability to perform occupational related tasks
- Objective lower extremity strength, range of motion (ROM), ankle brachial index (ABI) blood pressure, palpation, leg length, foot parameters tests

10.3 At any point in the study, will you request, use, or access health information in any form, including verbal, hard copy and electronic?

☒ Yes ☐ No

10.4 Review the definitions below and respond to the following two questions. If you are not sure of the answers, email [contact] for assistance. The *Military Health System (MHS)* is defined as all DoD health plans and DoD health care providers that are organized under the management authority of, or in the case of covered individual providers, assigned to or employed by, the Defense Health Agency (DHA), the Army, the Navy, or the Air Force. *MHS workforce members* are employees, volunteers, trainees, and other persons whose conduct, in the performance of work for the MHS, is under the direct control of the MHS, whether or not they are paid by the MHS. *MHS business associates* are persons or entities that provide a service to the MHS and require protected health information (PHI) to provide the service.

Are you an MHS workforce member?

- ☒ Yes, I am an MHS workforce member
☐ No, I am not an MHS workforce member

10.5 Have you consulted with an MHS data expert to determine the data elements required for your study?

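### The 3-month satisfaction answer and, less directly, the 2-mile run overlap with the criteria for the treatment offer, which could favour supervised gait retraining (Group 2 v 1, Group 4 v 3) at the last blinded visit

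*Combined protocol and SAP*

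**What the plan says.** **The offer (10.1, Study Blinding).** Once the 3-month visit is complete and the blind is lifted, the plan makes an offer to a group it defines as "Participants who are not satisfied with their treatment results and/or who are unable to complete a 2-mile run without producing pain and/or symptoms". The offer is of BoNT-A, supervised gait retraining or both, limited to whichever of the two the person has not yet had. The two criteria are joined by and/or, so either one is enough. The section does not say on which form dissatisfaction is judged, or whether it is judged before or after the injection is revealed.

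**The outcomes (10.2).** The primary list ends with "ability to return to full active duty, and ability to complete a 2-mile run". Satisfaction is a secondary outcome: "patients will be asked if they were or were not satisfied with intervention at each follow up time point". The run comes from a "self-paced treadmill test until cessation or the successful completion of a two-mile run" (10.1, Follow Up Data Collection).

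**The time points.** Hypothesis 3 in 9.3 assesses the run and fitness tests "within the established standards at 8 weeks, 3 months, 6 months, and 12 months post-study injection". No time point is named as primary.

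**The blind.** It covers the injection only: "Participants will be blinded to assigned treatment arm (i.e., saline vs. BoNT-A injection) until 3 months post-injection". Home-based participants have a single in-person therapy session and supervised participants have a course of them (10.1), so each participant knows which gait programme they received.

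**The concern.** Two results the trial will analyse are close to the criteria that decide who is offered more treatment. Both depend on the participant: the treadmill test is self-paced and ends when they stop, symptoms are self-reported, and satisfaction is yes or no. Someone who wants the treatment they lack has a reason to report a poorer result.

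That reason is not the same in every arm. Home-based participants know there is something for them; supervised participants do not. Lower reported success in the home-based arms would look like a benefit of supervised retraining. It would arise at the last visit before unblinding and crossover, so later visits cannot replace the comparison. Completing the visit before unblinding protects against knowledge of the injection, but nothing in the plan separates the outcome answer from the offer.

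**Working it through.** **1. What each participant can expect from qualifying.** Allocation is uniform across four arms (10.1, Randomization), so with the blind intact every participant has a 1/2 chance of having had saline.

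| Group | Treatments actually lacking | Expected gain as the participant sees it |
|---|---|---|
| 1 (home-based, saline) | 2 | 1 (SGR, certain) + 1/2 = 1.5 |
| 2 (supervised, saline) | 1 | 0 + 1/2 = 0.5 |
| 3 (home-based, BoNT-A) | 1 | 1 (SGR, certain) + 1/2 = 1.5 |
| 4 (supervised, BoNT-A) | 0 | 0 + 1/2 = 0.5 |

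The perceived gain differs within 2 v 1 (Hypothesis 2) and 4 v 3 (half of Hypothesis 3). It is equal within 3 v 1 (Hypothesis 1) and 4 v 2.

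**2. How closely the criteria match the outcomes.**
- Satisfaction: the criterion concerns treatment results and the outcome concerns the intervention. They are nearly the same question, and a negative answer alone qualifies.
- Run: the criterion is a run without pain or symptoms, while the outcome in 10.2 is completing the run. A participant can finish, count as an outcome success, report symptoms and still qualify. The sample-size endpoint in 11.5, passing the US Army 2-mile run test, is different again.

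Satisfaction is therefore the more exposed outcome.

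**3. Sensitivity of the error rate.** The plan gives no figure to reproduce here.

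Inputs: 120 evaluable per arm (11.2); significance at 0.05 (11.5), taken as two-sided; true success 50%, an illustrative value, or 69%, the share satisfied or somewhat satisfied in the retrospective review in 9.2. The share *a* of true successes reported as failures is an **assumption**; the documents give none.

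With no true effect and true rate p, the reported rates are p(1 − a₁) in the arm with more to gain and p(1 − a₂) in the other. The test is z = (p̂₂ − p̂₁) / √[p̄(1 − p̄) × 2/120], rejecting when |z| > 1.96. The rejection rate is the sum of the exact binomial probabilities of all rejecting outcomes.

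| p | a₁ v a₂ | Reported rates | Rejection rate |
|---|---|---|---|
| 0.50 | 0 v 0 | 0.500 v 0.500 | 0.045 |
| 0.50 | 10% v 0 | 0.450 v 0.500 | 0.114 |
| 0.50 | 20% v 10% | 0.400 v 0.450 | 0.123 |
| 0.50 | 20% v 0 | 0.400 v 0.500 | 0.335 |
| 0.69 | 0 v 0 | 0.690 v 0.690 | 0.049 |
| 0.69 | 10% v 0 | 0.621 v 0.690 | 0.203 |
| 0.69 | 20% v 10% | 0.552 v 0.621 | 0.195 |
| 0.69 | 20% v 0 | 0.552 v 0.690 | 0.607 |

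In the unequal rows nearly all rejections favour the arm with less to gain. Equal under-reporting of 10% or 20% in both arms gives 0.047 to 0.053.

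**4. At the planned rates** (11.5: 15%, 50%, 80% and 85% for Groups 1, 2, 3 and 4), with an assumed 10% under-reporting in both home-based arms and none in the supervised arms:
- 2 v 1: from 50 − 15 = 35 to 50 − 13.5 = 36.5 points.
- 4 v 3: from 85 − 80 = 5 to 85 − 72 = 13 points; the rejection rate rises from 18% to 70%.
- 3 v 1: from 80 − 15 = 65 down to 72 − 13.5 = 58.5 points.

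The contrast with the smallest planned difference is the most exposed, and Hypothesis 1 moves against the hypothesis.

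**The case against.** **The bias does not favour every hypothesis.** A reader might infer from the treatments actually lacking (2, 1, 1, 0) that Group 1 has most to gain, Group 4 least, and that all three hypotheses are favoured. The documents do not support this. That ordering follows the true allocation, which participants do not know when they run and answer. Extending it to 3 v 1 and 4 v 2 requires them to guess their injection. Section 9.2 offers a possible cue ("Eleven patients experienced reduced muscle strength", of 16), but from an uncontrolled series that describes the weakness as transient and of no functional consequence. Guessing is possible, not shown.

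**Nobody has to fail the run.** A reader might also infer that a participant must perform badly to get the offer. Either criterion suffices, and the run criterion is stricter than the run outcome. This stands, and it is why the point rests mainly on satisfaction.

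**The motive is assumed.** The available text does not say that participants know of the offer beforehand, and the consent form is not available. Section 14.6 points the other way: health information may go to command for fitness-for-duty evaluation, which could encourage over-reporting of success. Both stand as limits.

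**The shares are invented, and 69% is not a yes/no rate.** True. It pools satisfied with somewhat satisfied in an uncontrolled BoNT-A review. The table shows sensitivity and is not an estimate.

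What remains is the overlap between outcome and criterion, the known difference between gait-training arms, and the absence of any separation between the two uses.

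**Conclusion.** The point holds as a conditional concern, mainly about satisfaction, for Group 2 v 1 and Group 4 v 3 at 3 months. It requires that participants know of the offer in advance and that some respond to it. The BoNT-A contrasts are affected only if participants also guess their injection.

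The size cannot be derived from the documents. Under the assumed 10% to 20% one-sided under-reporting, a nominal 5% test rejects about 11% to 34% of the time at 50% true success and 20% to 61% at 69%. If under-reporting is equal across arms, there is almost no inflation. How much weight the 3-month visit carries is also open, since no primary time point is set. The change is worth making because it is cheap and cannot be made after the 3-month data are collected.

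**What to change.** Leave the offer, and who qualifies for it, as written. In 10.1, Study Blinding:

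1. Require the 3-month Follow Up CRF, including the satisfaction outcome, and the treadmill run to be completed and locked first.
2. Then record dissatisfaction for the purpose of the offer as a separate question on a separate form, **before** the injection assignment is revealed. Asked afterwards, knowledge of having had saline could change who qualifies and add crossovers.
3. Tell participants beforehand that the outcome questionnaire is not used for the offer, and that they need not fail the run to qualify.

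In 11.1, the same contrasts at 8 weeks may be reported as supporting data, because no offer follows that visit. A difference that widens between 8 weeks and 3 months should not be read as evidence of bias: gait retraining may start 2 weeks or more after injection (10.1), so at 8 weeks participants have had at most about 6 weeks of it, and widening may simply be the training effect.

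Cost: one extra question and one sentence for participants. The run remains a route to the offer, so the incentive is reduced, not removed.
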